4.8.5 Incidental Gluten Exposure

A by-subject listing will be provided by study part and treatment group for any incidental gluten exposure (Yes/No) on enrolled subjects. Number of times the subjects is exposed to gluten within the study period will be calculated.

4.8.6 Medications for Infusion Reactions

A by-subject listing will be provided by study part and treatment group for any medications to treat infusion reactions by ATC levels and PT on enrolled subjects.

4.8.7 Study Drug Administration and Compliance

A by-subject listing for study drug administration and compliance will be provided by study part and treatment group on enrolled subjects.

4.8.8 Gluten Challenge Compliance

Patient compliance with GC will be listed as well as number of GC completed (Part B only).

For Part B (MAD), by-subject listings for the GC compliance will be provided on enrolled subjects.

4.9 Pharmacokinetics

All pharmacokinetic summaries and analyses will be on PKAS.

4.9.1 Pharmacokinetic Concentrations

Plasma concentrations for KAN-101 will be summarized by treatment group, day of dose, and nominal protocol timepoint for PKAS in Part A (SAD) and Part B (MAD) separately. Additionally, PK concentrations for Day 1 in 0.15, 0.30, and 0.60 mg/kg dose levels in Part A and B will be combined to summarize by treatment group, day of dose, and nominal protocol timepoint using descriptive statistics.

A by-subject listing for plasma concentration data for KAN-101-01, will be listed by study part, treatment group, subject, day and time of sampling for PKAS. Listings will include nominal and protocol time, actual sampling time relative to start and end of infusion, actual infusion duration, scheduled infusion duration (30 minutes) and difference between scheduled and actual infusion duration.

Following will be presented for Part A and Part B:

- Linear mean (+/- SD) plasma concentration-time profiles for KAN-101 by Day of dose (all doses on one plot)
- Semilogarithmic mean (+/- SD) plasma concentration-time profiles for KAN-101 by Day of dose (all doses on one plot)
- Linear individual concentration-time combined profiles for KAN-101 by Day of dose (all subjects on same dose on one plot)
- Semilogarithmic individual concentration-time combined profiles for KAN-101 by Day of dose (all subjects on same dose on one plot)
- Linear individual concentration-time profiles for KAN-101 (separate plot for each subject)
- Semilogarithmic individual concentration-time profiles for KAN-101 (separate plot for each subject)

4.9.2 Pharmacokinetic Parameters

PK parameters for KAN-101 will be summarized by study part, treatment group and day of dose For Part A and Part B separately, using the PKAS.

Additionally, Part A and B parameters will be pooled for the first (Day 1) dose for doses common in Parts A and B for summary tables and plots.

- Descriptive statistics for calculated PK parameters will include n, arithmetic mean, SD, %CV, geometric mean, geometric CV% (calculated as: $\text{geometric CV\%} = \text{SQRT}(s^2 - 1) * 100$; where s is the standard deviation of the log-transformed values), median, minimum and maximum values.
- For t_{max} , only median, minimum and maximum values will be presented.
- λ_z or Lambda_z dependent PK parameters, i.e. λ_z , $\text{AUC}_{0-\text{inf}}$, CL, V_z will not be summarized if r^2_{adj} is <0.90 , and/or span of the terminal phase is <1.3 times the half-life and/or the %extrapolation to calculate $\text{AUC}_{0-\text{inf}}$ is $>30\%$, unless otherwise determined by the PK scientist. Such parameters will be flagged in parameters listing, and if flagged parameters are not used for calculation of descriptive summaries, it will be footnoted in the PK parameters listing.

A by-subject listings for PK parameters and dose-normalized PK parameters for KAN-101-01 will be listed by study part and treatment group, subject and day of dose using the PKAS.

[figure not shown]

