12.9. Pharmacokinetic Analyses

Blood samples will be collected for measurement of KAN-101, as specified in [Table 1](#) and [Table 2](#). The timing of sampling may be altered based on the emerging PK data. The adjustment of the PK sampling schedule is not considered to be a substantial amendment so long as the total number of plasma PK samples and the total blood volume to be collected from each participant will not change. Any adjusted sampling time points will be documented appropriately.

Instructions for the collection and handling of biological samples will be provided by the Sponsor. The actual date and time of PK blood sampling will be recorded by the Investigator or designee in the CRF, as appropriate.

For the final analysis, PK parameters of KAN-101 will be determined from the plasma concentration-time data. Parameters will be calculated by noncompartmental modeling methods, using Phoenix WinNonlin 8.0 or higher, using actual sampling times where relevant. The parameters that will be calculated are defined in [Table 3](#), and will be calculated for single or multiple dosing of KAN-101, as appropriate. Not all listed parameters may be calculable, and additional parameters may be calculated, if needed, to fully characterize the available data.

[figure not shown]
Table 3: Pharmacokinetic Parameter Definitions

Parameter	Definition
C_{max}	Maximum observed plasma concentration
T_{max}	Time to first occurrence of maximum observed plasma concentration
C_{trough}	Pre-dose plasma concentration
AUC_{72}	Area under the plasma concentration-time curve from time 0 to 72 hours post-dose
AUC_{last}	Area under the plasma concentration-time curve from time 0 to the last measurable time point
AUC_{inf}	Area under the plasma concentration-time curve extrapolated to infinity
AUC_{tau}	Area under the plasma concentration-time curve over the dosing interval
$t_{1/2}$	Terminal elimination half-life
CL/F	Apparent oral clearance
V_z/F	Apparent volume of distribution after a single dose
$R_{acc,AUC}$	Accumulation ratio based on AUC
$R_{acc,Cmax}$	Accumulation ratio based on C_{max}

Statistical evaluations of PK data will include dose proportionality assessment using C_{max} , AUC_{last} , and AUC_{inf} .

For cohort by cohort PK analysis, not all PK parameters may be calculated, and noncompartmental analysis done may be done using nominal times.

Additional details on the PK analyses will be provided in a PK analysis plan.

CCI

CCI

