4.3.2 PK Tables, Listings and Figures

The following rules will be followed with regards to the number of decimal places and presentation of data in the tables and listings for PK concentration data:

- Source data shall be used in all derived PK concentrations without prior rounding.
- The mean, SD, geometric mean and median will be tabulated to same significant digit compared to the source data, but with a maximum of four significant digits.
- Minimum and maximum values will be tabulated to the same precision as the source data, but with a maximum of four significant digits.
- Geometric coefficient of variation (geometric CV%) and arithmetic coefficient of variation (CV%) will be presented to one decimal place.

The following rules will be followed with regards to the number of decimal places and presentation of data in the tables and listings for PK parameters:

- Individual PK parameters will be presented to three significant digits, with the exception of t_{max} , which will be presented to three decimal places.
- Parameters derived directly from source data (e.g. C_{max}) shall be reported with the same precision as the source data (if this is not four significant digits).
- The mean, geometric mean, median and SD values will be reported to three significant digits, all other descriptive statistics will also be reported to three significant digits except for CV% and geometric CV% which will be presented to one decimal place.
- For t_{max} , the minimum and maximum will be presented to three decimal places and all other descriptive statistics will be presented to three decimal places.
- Estimates and confidence intervals in the form of percentages will be presented to two decimal places.

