4.4.4 Concentrations Below the Limit of Quantification (BLQ)

For PK data, all concentrations that are BLQ will be labeled as “BLQ” in the concentration data listings (Footnote describing the BLQ value will be added to the listing).

For summary: For concentration summary tables and mean concentration time plots, all BLQs will be considered zero, and the number of BLQs and non-BLQs at each scheduled time point will be reported.

For individual data: For non-compartmental PK analysis, all below the limit of quantification (BLQ) values pre-dose to the first dose, and prior to the first quantifiable concentration will be substituted by zeros. BLQ values between non-BLQ concentrations will be considered missing before the calculation of the PK variables. Terminal BLQ values will be considered missing.

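### As the text reads, the geometric CV% formula in SAP 4.9.2 lacks the exponential: it has no real value for s below 1 and is at most about 40% of the correct value above that

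*SAP*

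**What the plan says.** SAP 4.9.2 lists the summary statistics for the PK parameters: "Descriptive statistics for calculated PK parameters will include n, arithmetic mean, SD, %CV, geometric mean, geometric CV"%, followed by the median and range. In parentheses it defines the geometric CV% as a square root whose argument and scaling read "s^2 - 1) * 100$; where s is the standard deviation of the log-transformed values". The dollar sign is a remnant of text conversion. In plain notation the rule is SQRT(s² − 1) × 100.

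These statistics apply to the Part A tables, the Part B tables and the pooled Day 1 tables for the common doses. For t_max only the median, minimum and maximum are shown.

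The only other mention of the statistic's calculation or display is a rounding rule in SAP 4.3.2: "Geometric coefficient of variation (geometric CV%) and arithmetic coefficient of variation (CV%) will be presented to one decimal place". It gives no formula. The protocol gives none either; its section 12.9 says "Additional details on the PK analyses will be provided in a PK analysis plan". That plan and the table shells named in the SAP revision history are not among the documents at hand. Protocol section 12 lets the final SAP prevail where the two differ.

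**The concern.** For log-normal data, with s the SD on the natural-log scale, the coefficient of variation on the original scale is SQRT(exp(s²) − 1). The subtraction of 1 belongs to the exponential. Without the exponential, the expression is neither the exact formula nor its small-s approximation, which is simply s. It would be right only if s² stood for the exponential of the log variance, and the SAP defines s otherwise: "where s is the standard deviation of the log-transformed values".

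If the rule were programmed as it reads, the PK parameter tables would show either no geometric CV% or one that is much too small. The second case is the less visible, because the number would look plausible. Geometric CV% is a named summary of between-patient variability for the secondary endpoint.

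**Working it through.** **Inputs**
- Formula as it reads (SAP 4.9.2): G₁(s) = 100 × SQRT(s² − 1).
- Log-normal formula for the same s: G₂(s) = 100 × SQRT(exp(s²) − 1).
- Definition of s: SD of the log-transformed values (SAP 4.9.2). The base of the logarithm is not stated there; natural log is assumed.
- Size of s for KAN-101: not given in either document, so a range is shown.
- The documents state no numerical geometric CV%, so there is no figure to reproduce.

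**Step 1: where the formula has no value.** G₁ needs s² ≥ 1. At s = 0.5, s² − 1 = 0.25 − 1 = −0.75, which has no real square root. The boundary s = 1 corresponds to a true geometric CV of 100 × SQRT(e − 1) = 100 × SQRT(1.7183) = 131.1%. Conversely, s = SQRT(ln(1 + CV²)), so a true geometric CV of 30%, 50% or 100% means s = 0.294, 0.472 or 0.833. All three lie where G₁ does not exist.

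**Step 2: the two formulas side by side.**

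| s | s² − 1 | As it reads, G₁ | Correct, G₂ | G₁/G₂ |
|---|---|---|---|---|
| 0.3 | −0.91 | no value | 30.7% | – |
| 0.5 | −0.75 | no value | 53.3% | – |
| 0.8 | −0.36 | no value | 94.7% | – |
| 1.0 | 0 | 0.0% | 131.1% | 0 |
| 1.2 | 0.44 | 66.3% | 179.5% | 0.37 |
| 1.5 | 1.25 | 111.8% | 291.3% | 0.38 |
| 2.0 | 3.00 | 173.2% | 732.1% | 0.24 |

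For example, at s = 1.5, G₁ = 100 × SQRT(1.25) = 111.8%, and G₂ = 100 × SQRT(exp(2.25) − 1) = 100 × SQRT(8.488) = 291.3%.

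**Step 3: the closest the two come.** Put u = s². The squared ratio is (u − 1)/(exp(u) − 1). Setting its derivative to zero gives exp(u) × (2 − u) = 1, so u = 1.841 and s = 1.357. There G₁ = 92% and G₂ = 230%, a ratio of 0.398. For every other s above 1 the ratio is smaller.

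**Step 4: what else uses the statistic.**
- Geometric means, arithmetic CV%, medians, ranges and listings are computed without it.
- SAP 4.3 rules out inferential statistics.
- SAP 4.9.2.1 judges dose proportionality informally, from box plots of the parameters and their dose-normalized values.
- The stopping and escalation rules in protocol 4.9 count DLTs. The safety committee also sees available PK data, but no rule refers to a geometric CV.

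**The case against.** The strongest objection is that the SAP itself may be correct. The formula was typeset and then read from a PDF, and an e with a nested superscript is easily lost in that step. The surviving subtraction of 1, and the definition of s on the log scale, both fit an intended exp(s²) − 1. This objection stands as a limit on confidence. It does not remove the point, because the text does not show that a loss occurred. Other PK mathematics in SAP 3.5.2, such as the integrals, came through, as did the square in this formula. That is only weak evidence, since a nested exponent is more fragile. The PK analysis plan and the shells may also carry the right formula; that is unknown.

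The second objection is that a literal program would fail visibly: a negative argument gives a missing cell, and SAP 4.1 calls for an independent check of the outputs. This is fair for s below 1. It is weaker for s above 1, where a number appears.

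Three stronger readings are tempting, and the documents do not support them:
- *The SAP is certainly in error.* Only the source page can settle that.
- *Most cells will be blank, or most will be wrong.* How often either occurs depends on the log-SD of KAN-101 parameters, which neither document gives.
- *The PK conclusions or the escalation decisions are compromised.* Nothing in either document makes them depend on this statistic.

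**Conclusion.** The point holds as a minor one. On the text as it stands, the stated rule gives no real value for s below 1 (true geometric CV below about 131%), 0% instead of 131% at s = 1, and at most about 40% of the correct value above that. Nothing else in the protocol or SAP corrects it. The conclusion rests on two assumptions: that the logarithm is natural, and that the source page reads as the converted text does. The effect is confined to one descriptive statistic of the secondary PK endpoint; the primary safety endpoint is not touched.

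A separate matter should not be folded into this one. SAP 4.3.2 expects a geometric mean and geometric CV% for concentrations, while SAP 4.4.4 says "For concentration summary tables and mean concentration time plots, all BLQs will be considered zero". Zero has no logarithm, so any log-based geometric statistic is undefined at a time point with a BLQ value, whichever CV formula is used. The Day 1 pre-dose sample, taken before any drug is given, is the plainest case.

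**What to change.** Check the source page of SAP 4.9.2. If it shows exp(s²), no change is needed. If not, make the formula read: geometric CV% = SQRT(exp(s²) − 1) × 100, where s is the SD of the natural-log values. In either case, confirm that the PK parameter table programs use the exponential form. The cost is one look at a page, at most one edited line, and one program check. No data, design feature or other analysis changes.

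Raise the BLQ question as its own item: one sentence in SAP 4.4.4 saying how geometric statistics for concentrations are handled at time points with BLQ values.

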4.9.2.1 Assessment of Dose Proportionality

No formal dose proportionality assessment will be performed. Informal assessment of dose proportionality will be done using Box plots for C_{max} and AUCs and corresponding dose-normalized parameters by Part A, Part B, and combined parts A and B for the common doses.

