4.1. PART A – Single Ascending Dose

Part A employs a SAD 3+3 design, in which patients will receive a single IV infusion of KAN-101 on Day 1 (D1) followed by 20 days of safety monitoring, which includes assessment of AEs, clinical signs and symptoms, and clinical laboratory values.

All cohorts in Part A will employ sentinel dosing, whereby the first patient in each cohort will be dosed at least 7 days prior to the subsequent patients to monitor for the acute and subacute safety of KAN-101. Based on nonclinical data, a sentinel period of 7 days should be sufficient to allow for complete drug clearance (>5 half-lives) and development of the immune tolerance mechanism.

The doses for Part A include 0.15 mg/kg (Cohort 1), 0.3 mg/kg (Cohort 2), 0.6 mg/kg (Cohort 3), and 1.2 mg/kg (Cohort 4). After the last patient within a given dose cohort has been followed for at least 7 days post-dose, a safety review will be performed by the SMC and will include review of all available safety and PK information. Dosing at the next dose level will only commence upon a recommendation from the SMC and approval by the Sponsor.

For all patients in Part A, the study will consist of a 28-day screening period, a single dose of KAN-101 administered on D1 and follow up through D21. D1 includes a 10-hour monitoring period in the clinic/hospital unit and a phone call follow up approximately 24 hours after dosing.

- If a patient is experiencing active AE(s) which require clinical monitoring at the end of the clinic/hospital unit monitoring period, the patient should not be discharged and should be followed until satisfactory resolution as determined by PI
- If feasible, patients should be advised to have someone stay with them after discharge until 24 hours have elapsed after study drug administration on D1.
- If patients do not live within 1-hour travel time of an emergency medical facility, they should remain in the clinic/hospital unit for the first 24 hours after study drug administration.
- Patients should be instructed not to drive themselves to seek emergency medical treatment.

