12. STATISTICAL METHODS

Details of the statistical methods for this study will be documented in a Statistical Analysis Plan (SAP). When there is a difference between the final approved SAP and the protocol, the methods described in the final SAP will prevail.

Statistical methods will be primarily descriptive in nature. No hypothesis will be formally tested. For Part A, the data will be listed by dose group. For Part B, summary statistics will be provided by dose group. Categorical variables will be summarized using numbers and percentages. Continuous variables will be summarized by total number (n), mean, standard deviation (StD), median, and range (minimum and maximum).

Part A and Part B PK will be analyzed separately and together where appropriate.

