4.3 General Presentation Considerations and Descriptive Statistics

No formal statistical hypotheses or inferential statistics will be performed in this study. For Part A and Part B, summary statistics and listings will be provided by dose.

All by-visit summaries will be based on the nominal day/time per Appendix 6.1 [Table 8](#) (Part A) and [Table 9](#) (Part B) as recorded on the eCRF.

Study day will be calculated relative to the date of first dose, ‘Study Day’ = Assessment Date – First Dose Date + 1.

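### The SAP reduces the protocol's dose-proportionality evaluation to box plots without declaring the change, and plans no slope, ratio or interval

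*SAP*

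**What the plan says.** Protocol 12.9: "Statistical evaluations of PK data will include dose proportionality assessment using" Cmax, AUClast and AUCinf. It gives no model, interval or criterion, and adds: "Additional details on the PK analyses will be provided in a PK analysis plan". That plan is not among the documents reviewed.

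SAP 4.9.2.1: "No formal dose proportionality assessment will be performed". It continues: "Informal assessment of dose proportionality will be done using Box plots for" Cmax, the AUCs and their dose-normalized versions. Plots are made for Part A, for Part B, and for both parts combined at the doses they share. SAP 4.2, which is the place for departures from the protocol, reports none.

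Two general statements bear on this. Protocol 12 says: "Statistical methods will be primarily descriptive in nature. No hypothesis will be formally tested". SAP 4.3 goes further: "No formal statistical hypotheses or inferential statistics will be performed in this study". Protocol 12 also sets precedence: "When there is a difference between the final approved SAP and the protocol, the methods described in the final SAP will prevail".

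**The concern.** PK after single and multiple doses is the only secondary objective, and dose proportionality is the one PK evaluation that Protocol 12.9 singles out by name. A reader of the protocol expects some quantified statement of how exposure scales with dose. A reader of the SAP finds plots, and is told that nothing has changed.

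The plots are also narrower than the data allow. Protocol 12.1 plans to combine Part A PK with first-dose PK from Part B and does not limit this to certain doses. SAP 4.9.2 and 4.9.2.1 combine only the common doses of 0.15, 0.3 and 0.6 mg/kg. The 1.2 mg/kg group therefore appears only in the Part A plot, with 3 to 6 patients, and the combined view covers a 4-fold rather than an 8-fold range.

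At stake is how well the report can describe a departure from proportionality. Box plots with tabulated geometric means can show a gross departure. They do not say how large a modest one is, or how uncertain.

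**Working it through.** **The plan's own figures.** No PK precision figure is stated. The one sample-size figure (6 active patients per Part B cohort, 0.80, AE rate 0.25) corresponds to 1 − 0.75^6 = 0.822. It concerns AEs and has no bearing here.

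**Inputs from the documents.**
- Part A: 0.15, 0.3, 0.6 and 1.2 mg/kg, 3 to 6 patients each (Protocol 4.1 and 12.1, SAP 3.2). I take the minimum, 3 each, so 12.
- Part B, first dose: 0.15, 0.3 and 0.6 mg/kg, 6 active patients each, so 18 (Protocol 4.2 and 12.1, SAP 3.2).
- The Day 1 PK sampling times are the same in both parts (Protocol Tables 1 and 2).

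**Assumed.** Between-patient CV of 30%, 40% or 60%; log-normal exposure with equal log-scale variance at each dose; all 30 profiles usable.

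**Model.** ln(parameter) = a + b·ln(dose) + part, where b = 1 is proportionality. The 90% CI half-width for b is t(0.95, df) × s / √Sxx, with s = √ln(1 + CV²) and Sxx the within-part sum of squares of ln(dose).

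**Sxx.** Doses double, so the spacing is ln 2 = 0.693, with square 0.4805.
- Part A: 3 × (1.5² + 0.5² + 0.5² + 1.5²) × 0.4805 = 3 × 5 × 0.4805 = 7.207
- Part B: 6 × (1 + 0 + 1) × 0.4805 = 5.765
- Total 12.972, with root 3.602; df = 30 − 3 = 27; t = 1.703

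| Assumed CV | s | SE(b) | 90% half-width | Factor over 8-fold range, 8^half-width |
|---|---|---|---|---|
| 30% | 0.294 | 0.082 | 0.139 | 1.33 |
| 40% | 0.385 | 0.107 | 0.182 | 1.46 |
| 60% | 0.555 | 0.154 | 0.262 | 1.72 |

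Leaving out the part term changes little: 0.134, 0.176 and 0.254.

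**Comparisons.**
- Part A alone (12 patients, no part term): 0.198, 0.260 and 0.374.
- Both parts at the common doses only (27 patients): Sxx = 3 × 2 × 0.4805 + 5.765 = 8.648. The half-widths are about 0.17, 0.22 and 0.32, roughly 23% wider than with all doses (√(12.972/8.648) = 1.22, plus a slightly larger t).

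**Could the data establish proportionality?** A conventional criterion asks that the 90% CI for b lie within 1 ± ln(1.25)/ln(8), that is 0.893 to 1.107. Even centred on 1, an interval of the expected width fails at 30% CV, because 0.139 exceeds 0.107. In simulation with true b = 1 (200,000 draws, model without the part term), the chance of meeting the criterion with 30 patients is 26% at 20% CV, 0.5% at 30% and about zero from 40%. With Part A at its maximum (42 patients) it is 59% at 20% CV and 7% at 30%. The part term makes these slightly lower.

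**The case against.** The strongest reply is that the protocol promised only an assessment. It names no model, describes its methods as mainly descriptive, and lets the SAP prevail. Plots of raw and dose-normalized exposure by dose are a defensible descriptive assessment. That stands: a reader might infer that the SAP broke a commitment to a formal analysis, and the documents do not support this. But the precedence rule settles which method governs. It does not make SAP 4.2 accurate.

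A reader might also infer that the PK question gets no estimate of any kind. That goes too far. SAP 4.9.2 tabulates geometric means and geometric CVs by dose and day, with pooled Day 1 tables for the common doses, and lists dose-normalized values by patient. What is missing is a slope or ratio with an interval. Summary tables of dose-normalized values are not explicit, and SAP 3.5.2 leaves the choice of reported parameters to the PK scientist.

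The separate PK analysis plan might contain a model. If it does, the flat statement in SAP 4.9.2.1 conflicts with it and still needs correcting.

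Finally, SAP 4.3 excludes inferential statistics, so a confidence interval sits awkwardly with it. That is fair, and the fix has to deal with it. SAP 4.3.2 does already set a display format for estimates and confidence intervals given as percentages, so intervals are not foreign to the document.

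**Conclusion.** The point holds as an undeclared reduction in method for a named evaluation under the secondary objective, together with a missed and inexpensive estimate. The primary safety analysis is unaffected.

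On the assumed CVs, the planned data give b to within about ±0.14 to ±0.26. At 40% CV, an estimate of b = 1 would leave exposure at the top of the 8-fold range between about 0.68 (1/1.46) and 1.46 times proportional. This is useful as description. It should not be read as the data being able to settle proportionality: by conventional limits that is unlikely at these sample sizes unless CV is about 20% or lower, and even then far from assured.

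The CV range is an assumption throughout. The half-widths are best case for AUC0-inf, because SAP 4.9.2 normally leaves out of the summaries profiles with adjusted r² below 0.90, a terminal span under 1.3 half-lives, or extrapolation above 30%. Fewer usable profiles mean a wider interval.

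**What to change.** 1. **SAP 4.9.2.1.** Add a descriptive power model, ln(parameter) = a + b·ln(dose) + part, for Day 1 Cmax, AUC0-t and AUC0-inf, pooled over Part A and the first dose of Part B and over all doses. Report b with a 90% CI and the number of profiles used, with no test and no verdict on proportionality. Keep the box plots.
2. **Same section.** State whether the single 1.5 mg/kg patient, a Part A reporting group in SAP 4, enters the model. Inclusion widens the dose range to 10-fold and makes one patient the sole support at the top.
3. **SAP 4.3.** Amend the wording so that intervals given as description are allowed.
4. **SAP 4.2.** Replace the declaration of no changes with a statement of how the method differs from Protocol 12.9, and why. This is needed even if the model is not adopted.

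The cost is one regression per parameter on data already collected, and a few sentences of text. The downside is that the interval may be wide, so it must be labelled descriptive to keep a wide interval around 1 from being read as proof of proportionality.
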